**Master Protocol – Summary of changes from previous version**

Version	V. Date	Revision summary	PRC status	IRB status
1.0	03/01/2021	n/a – Initial submission	accrual tracking only, PRC not required.	Approved on 06/14/2021
2.0	6/22/2021	The patient recruitment process has been updated. Patient records will be accessed by genetic counselors to identify potential participants to be contacted about the study opportunity. A partial waiver of HIPAA authorization is being requested, and the data sources, recruitment questions, and study protocol have been updated to reflect the revised recruitment plan. The verbal consent scripts have been revised to emphasize that the enrollment call is related to the study opportunity previously shared with the participant. The information sheets have been updated to identify OSU as a collaborator.	accrual tracking only, PRC not required.	Approved on 9/1/2021
3.0	11/3/2021	Modifications to the recruitment and informed consent process for participants, informed consent will be gathered from patients and genetic counselors who wish to provide feedback on using the workbook before conducting a follow up interview and survey. Patients and genetic counselors will still be contacted by email to introduce the study opportunity. However, the email will only discuss providing feedback about the workbook as part of the simplified consent process that does not disrupt genetic counselor workflow.	accrual tracking only, PRC not required.	Approved on 1/13/2022
4.0	2/1/2022	Ohio State University was added as a second site and study was updated to a multi-site study.	accrual tracking only, PRC not required.	Approved on 2/28/2022

5.0	3/28/2023	
The recruitment strategy was expanded. In addition to patients with Lynch Syndrome being recruited through genetic counselors at Ohio State University and UNC Chapel Hill, newly diagnosed patients will also be recruited through the Lynch Syndrome International (LSI) Facebook community due to personnel changes and recruitment delays at OSU. An advertisement will be posted on the LSI Facebook page to share the study opportunity, and patients with Lynch Syndrome who see the advertisement will be able to email to join the study. Verbal consent will be collected for patients recruited through LSI using an updated verbal consent script that accounts for this modification.
	accrual tracking only, PRC not required.	Approved on 5/12/2023
6.0	6/20/2023	
The eligibility criteria were changed. Instead of calling patients to assess initial eligibility, an online survey link (using REDCap) will be sent in response to their interest email, which includes eligibility criteria (see attached Eligibility Screener). Additionally, sociodemographic items will be included in this survey to meet enrollment goals and ensure representative enrollment by race, ethnicity, and gender. Once eligibility has been determined, follow-up will be conducted by the research assistant via email to schedule a call with the eligible participant to complete informed consent or to inform them that they are not eligible to participate in the study.
	accrual tracking only, PRC not required.	Approved on 6/28/2023

7.0	5/29/2025	
Several updates were made to the protocol to reflect changes in the recruitment approach:
 
(1) the analysis software was changed from Atlas.ti to NVivo
 
(2) the language was revised to refer only to patients, removing references to genetic counselors given that recruitment approaches changed
 
(3) Section 7.2 was updated to list only the UNC IRB as the IRB of record.
 
These changes were necessary due to earlier modifications in the recruitment strategy. No patients were recruited from Ohio State University due to personnel changes and recruitment delays. As a result, recruitment through the Lynch Syndrome International (LSI) Facebook community was prioritized over recruitment through genetic counselors.
	accrual tracking only, PRC not required.	6/06/2025
-----	-----------	--	--	-----------

### **Protocol Amendment (v7. 06062025)**

#### Summary of Changes:

- Recruitment procedures were updated to include Lynch Syndrome International's social media page as a recruitment site.
- Participants were recruited through Lynch Syndrome International.

- Recruitment through Lynch Syndrome International was prioritize over genetic counselors' recruitment.
- No patients were recruited from OSU due to personnel changes and recruitment delays.

Consents:

- Updated verbal consent script for patients recruited through LSI.

LCCC 20-3115

PI:[name]

Version/Date

## 1. BACKGROUND AND RATIONALE

### 1.1. Study Synopsis

We will trial an educational workbook on family cascade screening for individuals diagnosed with Lynch Syndrome, a genetic predisposition for certain types of cancer. Up to 5 genetic counselors at Ohio State University (OSU) and the University of North Carolina at Chapel Hill (UNC Chapel Hill) as well as 15 patients at OSU, University of North Carolina at Chapel Hill (UNC Chapel Hill), and Lynch Syndrome International (LSI) will pilot test the workbook and we will conduct surveys and qualitative interviews to understand the feasibility, acceptability, practicality, and economic impact of the workbook. The research team developed the workbook in a previous project using implementation science strategies to identify and develop an intervention for barrier and facilitators to family screening for Lynch Syndrome.

### 1.2. Background

An estimated 1 million people in the US have Lynch Syndrome (LS), a genetic disorder that increases lifetime risk for several cancers including up to 82% for colorectal cancer (CRC) and 60% for endometrial cancers (compared to 4% and 3% in the general population, respectively). Universal testing of all CRC and endometrial cancer patients for LS is an effective approach for identifying affected individuals and reducing their risk of subsequent cancers through enhanced screening and primary prevention strategies. The cost effectiveness of universal testing for LS hinges on cascade screening, the systematic identification and testing of family members of affected individuals. Unfortunately, many family members of patients with LS do not receive cascade screening. In previous research, we identified barriers to cascade screening including low knowledge, skills, and self-efficacy and perceived barriers such as family dynamics, cost, and fear of discrimination. We also identified facilitators including expectations of positive outcomes from communicating with family members and options for free family member testing. We used intervention mapping to identify an intervention that targets actionable barriers and facilitators to improve cascade screening uptake for LS.

### 1.3. Purpose and Rationale

The objective of this project is to test the feasibility and implementation of our intervention, an educational workbook on the importance of cascade screening for Lynch Syndrome families. Fifteen patients diagnosed with Lynch Syndrome will test the workbook. We will assess the success of the workbook as a tool to improve cascade screening through post-intervention surveys and a qualitative interview. This feasibility study will provide foundational knowledge on the usefulness and acceptability of the workbook to inform an R01 to test if the intervention can improve cascade screening uptake when

used in the clinical environment.

## 2. STUDY OBJECTIVES AND ENDPOINTS

### 2.1. Primary Objective

The primary research question is: Is Let's Talk, an educational workbook on cascade screening for individuals diagnosed with Lynch Syndrome, a feasible intervention for health professionals to improve family testing for Lynch Syndrome?

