## 4. STUDY PLAN

### 4.1. Study Design

This is a nonrandomized, multi-center, interventional feasibility study on the use of an educational workbook to improve cascade screening among individuals diagnosed with Lynch Syndrome. The study is a single arm, interventional trial of 15 patients diagnosed with Lynch Syndrome who are (1) patients of genetic counselors at Ohio State University Comprehensive Cancer Center or UNC Health System or (2) are member of the LSI Facebook page and up to 5 genetic counselors at Ohio State University Comprehensive Cancer Center or UNC Health System. The primary purpose of this study is to evaluate the feasibility of an educational workbook for Lynch Syndrome patients to improve family genetic testing. We anticipate study enrollment will take approximately 24 months, cumulative patient active participation will last approximately 10 months, and genetic counselor active participation will last

approximately 24 months. Individual patient participation duration will be approximately 1 month. The feasibility of the intervention workbook will be assessed through template analysis of qualitative interviews guided by CFIR^1 and quantitative survey design by the research team with scales to assess the costs of workbook use, knowledge, perceived knowledge, acceptability, and self-efficacy.

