All patient information will be tracked in a project in UNC's REDCap. All follow up interviews for patients will be conducted via Zoom. All follow up surveys for patients will be conducted electronically in REDCap.

For questions specifically related to genetic counseling or care management, patient participants should contact their site-specific genetic counselor or personal healthcare provider. For all other questions and concerns at any point in the study, participants recruited from OSU or UNC should contact the UNC research team. Questions about study eligibility and responsibilities should be directed to the UNC research team. If participants have questions or concerns about their rights as a research subject, or if they would like to obtain information or offer input, they can also contact the UNC Institutional Review Board at [contact] or by email to [IRB\\[contact]](mailto:[contact]).

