#### 4.7. Statistical Considerations

##### 4.7.1. Sample Size and Accrual

With up to five genetic counselors across sites or through LSI, we will enroll 15 Lynch Syndrome patients. The study personnel have conducted previous qualitative research on genetic testing for cancer care, including Lynch Syndrome. Thematic saturation in those studies was reached through 15 interviews with patients and providers. Thus, we expect to reach thematic saturation on the feasibility of the workbook for patients in the template analysis process by enrolling approximately 15 patients in the pilot study. Because we are working with a small number of patients for a rare disease, we anticipate working with a small number of genetic counselors. We expect general feasibility feedback from providers on the workbook.

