#### 4.9. Removal of Patients from Protocol

Any patient or genetic counselor who indicates they no longer wish to use the workbook or provide feedback on the workbook for any reason can notify the Principal Investigator at the UNC or the co-PI at OSU or another member of the research team who will inform the site PI and the participant will be removed from the study.

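### The only objective asks about feasibility for health professionals, but the plan can speak only to patient use, and its cost survey assumes a counseling appointment that self-directed participants did not have for the workbook

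*Combined protocol and SAP*

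**What the plan says.** Section 2.1 asks whether the workbook is "a feasible intervention for health professionals to improve family testing for Lynch Syndrome". Section 2.2 states that there are no secondary objectives. Sections 1.1, 4.1 and 4.2 include up to 5 genetic counselors, section 4.4 allots them about 4 to 20 hours of study activity, and section 4.7.1 adds "We expect general feasibility feedback from providers on the workbook".

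Other sections describe a study of patients. Section 4.1 says "The primary purpose of this study is to evaluate the feasibility of an educational workbook for Lynch Syndrome patients to improve family genetic testing". Section 1.3 has fifteen patients test the workbook, and section 4.7.1 justifies the sample size with "we expect to reach thematic saturation on the feasibility of the workbook for patients in the template analysis process".

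Section 4.2 describes two delivery routes. At the university sites the counselor works through the first prompt with the patient and explains the rest. Participants who come through the LSI Facebook page get the workbook from the research team after the enrollment call and complete it alone. The cost survey in 9.5 is worded for the first route only. Section 4.7.2 plans no description by route.

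**The concern.** Two things are at stake.

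The first is what the study may conclude. With one objective and no secondary ones, a report that follows section 2.1 literally would answer a question about health professionals without data from any. Section 1.3 says "This feasibility study will provide foundational knowledge on the usefulness and acceptability of the workbook to inform an R01", and that later study is meant to test the workbook in the clinical environment. Its readers will want to know whether a favorable result describes counselor-guided use or use by people working alone.

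The second is the cost data. Section 1.1 lists economic impact among the things the study sets out to understand. LSI participants are asked about a counseling appointment as though the workbook had been handed over there. They need only have been diagnosed within 365 days (3.1.2) and belong to the LSI page (3.1.4). Some may have seen a counselor elsewhere, for reasons unrelated to the workbook, and could answer about that visit.

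**Working it through.** There is no planned figure to reproduce: the 15 patients rest on thematic saturation, not on a power calculation. The check is whether objective, data and analysis match.

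**1. Who supplies data**

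- Appendices: 9.1 to 9.5 are five instruments, all for patients. Provider-completed: 0 of 5.
- Scales tested in 4.7.2: acceptability 7 + self-efficacy 5 + knowledge 7 + perceived knowledge 7 = 26 items, all in the patient survey. Provider-completed: 0 of 4 scales.
- Interview guide 9.1: 7 + 4 + 3 + 4 = 18 main questions or measures, plus 4 sub-probes (1a, 1b, 3a, 6a) = 22, leaving out the closing question. None names the counselor. One (3a) is specific to LSI participants.
- Follow-up: 4.2 describes it for patients, for example "All follow up surveys for patients will be conducted electronically in REDCap". In section 5 the only interview or survey entry is labelled as the patient's.
- Generic mentions: 1.1 says counselors and patients "will pilot test the workbook and we will conduct surveys and qualitative interviews", and 4.9 covers "Any patient or genetic counselor who indicates they no longer wish to use the workbook or provide feedback on the workbook". Neither names an instrument, a time point or an analysis.

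**2. Cost items in 9.5, read as an LSI participant would**

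| Item | Asks about | Consequence for an LSI participant |
|---|---|---|
| Preamble | Resources used from the counseling appointment onward | Wrong starting point |
| 1 | Purchases needed to attend the appointment | May report an unrelated visit |
| 2 | Distance and travel time to the counselor | May report an unrelated counselor |
| 3 | Time using the workbook with the counselor | Should be zero or not applicable |
| 4 | Whether time was taken off work to talk with the counselor | May report an unrelated visit |
| 5 | Hours off work to learn about the workbook from the counselor | Should be zero or not applicable |
| 6 | Time to go through the exercises | Answerable; misleading lead-in |

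Items that presuppose an appointment or a counselor: 6/19 = 31.6%. Items open to miscounting: 3/19 = 15.8%. Items 7 to 19 do not depend on the participant's own appointment.

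**3. How many responses could be affected**

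Let k be the number of LSI participants among 15. The responses open to miscounting number at most 3k, out of 19 × 15 = 285 in all. The documents do not give k, and 4.2 sets no minimum or maximum per site. At k = 15 the ceiling is 3 × 15 = 45. The version 7 change summary says that participants were recruited through LSI, so k is not zero. How many of them had a counselor elsewhere is unknown.

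**4. Whether provider data could support a test**

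They could not. With 5 counselors and no ties, the smallest two-sided exact signed-rank p is 2/2^5 = 0.0625, above an assumed 5% level. If 4 of 5 were favorable (an assumed result), the Clopper-Pearson 95% interval would be 28% to 99%. Any provider result would be descriptive, which favors narrowing the claim over adding a measure late.

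**The case against.** The strongest reply is that this is a matter of wording. A feasible intervention for health professionals can mean a tool that professionals hand to patients and that is judged through patients. Sections 1.3 and 4.1 read that way, and 4.7.1 promises only general provider feedback. This stands far enough to rule out a flat contradiction. It does not remove the need to reconcile the text: LSI participants use the workbook with no professional involved, so their ratings cannot inform delivery by professionals.

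Provider data collection might also appear in the 4.3 schema, which is not shown, or in the section 5 table, whose layout is lost. The finding is therefore limited to the readable text.

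Description by route may be called a reporting preference at this sample size, and one group may be small or empty. That is fair as regards tests. A count per route costs nothing, and readers need it to interpret the pooled results. It is also true that cost is not among the four tested outcomes, so no planned test changes.

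A reader might infer three further faults that the documents do not support:

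- **Item 6 cannot be answered by LSI participants.** It asks for a duration, which they can give, and question 3 of 9.1 asks the same in neutral words.
- **LSI follow-up has no time anchor.** One sentence in 4.2 counts from receipt from the counselor, but 4.6 covers both routes with a follow-up at about 4 weeks. Only a small wording alignment remains.
- **The integration theme is left unmeasured.** It has no heading of its own in the guide, but 4.7.2 treats the expected themes as provisional and allows them to be modified or removed.

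**Conclusion.** The point holds in two limited parts. First, the stated objective and the provider-feedback expectation go beyond the data: 0 of 5 appendices and 0 of 4 tested scales come from providers, so the study can conclude only about feasibility of patient use. Second, the 9.5 preamble and 6 of 19 cost items do not fit LSI participants, and items 1, 2 and 4 could bring unrelated counseling costs into the workbook cost summary.

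The planned comparisons of patient scores with their thresholds are untouched. One should not infer that the feasibility question as a whole is unanswerable, or that every participant came through LSI: the change summary gives no number by route. The actual size of any cost error is unknown, because it depends on that number and on how many LSI participants had a counselor elsewhere. The conclusion assumes that no counselor instrument sits in the material that cannot be read. It deserves correction before results are reported.

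**What to change.** Make one dated amendment that states recruitment status at the time of the change.

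1. **Objective.** Reconcile 2.1 and 4.7.1 with 1.3 and 4.1 by limiting the objective to feasibility of patient use. If the team prefers not to reword the objective this late, state that limit on the conclusion in 4.7.2. Align the counselor-participant text in 1.1, 4.1, 4.2, 4.4 and 4.9 as well; otherwise counselors remain participants with no stated purpose.
2. **Cost survey.** Treat items 1 to 5 as not applicable for LSI participants, and reword the preamble and item 6 to start from receipt of the workbook. If responses are already in, exclude or flag the counselor items for LSI participants and summarise costs by route. Bring the follow-up sentence in 4.2 into line with 4.6.
3. **Reporting.** In 4.7.2, commit to the number of participants by delivery route. Where both groups are non-empty, add descriptive scale summaries by route, without tests.

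This takes wording edits and one descriptive table, with no new patients or patient procedures. The drawbacks are a narrower claim to carry into the R01, route groups that may be small or empty, and a late wording change that must be disclosed.

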### 2.2. Secondary Objectives

There are no secondary objectives in this study.

## 3. PATIENT ELIGIBILITY

### 3.1. Inclusion Criteria

- 3.1.1. Participants must meet all of the following inclusion criteria to participate in the study.
- 3.1.2. Patients must have been diagnosed with Lynch Syndrome within the last 365 days.
- 3.1.3. Patients must be age 18 or older.
- 3.1.4. Patients must be receiving care from genetic counselors at UNC Health System OR OSU OR be a part of the Lynch Syndrome International advocacy group Facebook page.
- 3.1.5. Patients must be able to speak and read in English.
- 3.1.6. Patients must review informed consent documents and provide verbal consent to participate in the follow up interview and survey.

### 3.2. Exclusion Criteria

- 3.2.1. There are no exclusion criteria for study participants.

## 4. STUDY PLAN

### 4.1. Study Design

This is a nonrandomized, multi-center, interventional feasibility study on the use of an educational workbook to improve cascade screening among individuals diagnosed with Lynch Syndrome. The study is a single arm, interventional trial of 15 patients diagnosed with Lynch Syndrome who are (1) patients of genetic counselors at Ohio State University Comprehensive Cancer Center or UNC Health System or (2) are member of the LSI Facebook page and up to 5 genetic counselors at Ohio State University Comprehensive Cancer Center or UNC Health System. The primary purpose of this study is to evaluate the feasibility of an educational workbook for Lynch Syndrome patients to improve family genetic testing. We anticipate study enrollment will take approximately 24 months, cumulative patient active participation will last approximately 10 months, and genetic counselor active participation will last

approximately 24 months. Individual patient participation duration will be approximately 1 month. The feasibility of the intervention workbook will be assessed through template analysis of qualitative interviews guided by CFIR^1 and quantitative survey design by the research team with scales to assess the costs of workbook use, knowledge, perceived knowledge, acceptability, and self-efficacy.

#### 4.2. Study Recruitment and Activities

The recruitment goal for genetic counselors is up to 5 genetic counselors. The recruitment goal for patients with Lynch Syndrome is 15 total patients between OSU, UNC, and LSI. There is no minimum or maximum number of patients that can be enrolled at each site up to the goal of 15 patients total.

At OSU and UNC, the co-PI or another member of the research team will contact genetic counselors who work with Lynch Syndrome patients via email and notify them of the study opportunity and provide an information sheet. Interested genetic counselors will use the workbook with their Lynch Syndrome patients as a support tool for their standard cascade screening. The genetic counselors will provide the workbook to patients likely to test positive for Lynch syndrome or patients who have already been confirmed to have Lynch syndrome. If the patient is positive for Lynch syndrome, during a counseling call/appointment, the genetic counselor will complete the first prompt of the workbook to identify family members with the patient and explain the other sections of the workbook. Patients will complete the other sections of the work independently. The genetic counselor will notify the patient that the workbook creators are interested in hearing feedback on the workbook use and if the patient is interested, the genetic counselor will send the name, phone number, and email address of the patient to the UNC research team via secure email.

Through the LSI Facebook page, the study team will post an advertisement for patients recently diagnosed with Lynch Syndrome. Interested patients will reach out to the UNC research team by emailing the address posted in the study advertisement.

[figure not shown]
For all patients referred by a genetic counselor or self-referred, the UNC research team will schedule and complete a study enrollment call to answer questions, confirm eligibility, and document informed consent to participate in a follow up interview and survey. For patients directed to the study from the LSI Facebook page advertisement, the UNC research team will provide the workbook following the enrollment call and the participant will complete the activities in the workbook independently.

The UNC research team will complete the follow up interview and survey with patients approximately 4 weeks after they received the workbook from their genetic counselor.

All patient information will be tracked in a project in UNC's REDCap. All follow up interviews for patients will be conducted via Zoom. All follow up surveys for patients will be conducted electronically in REDCap.

For questions specifically related to genetic counseling or care management, patient participants should contact their site-specific genetic counselor or personal healthcare provider. For all other questions and concerns at any point in the study, participants recruited from OSU or UNC should contact the UNC research team. Questions about study eligibility and responsibilities should be directed to the UNC research team. If participants have questions or concerns about their rights as a research subject, or if they would like to obtain information or offer input, they can also contact the UNC Institutional Review Board at [contact] or by email to [IRB\\[contact]](mailto:[contact]).

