#### 4.6. Follow Up

After a genetic counselor has provided the contact information of an interested patients or the patient has directly contacted the research team by email, the UNC research team will reach out to the patient in approximately 1 weeks to gather informed consent and will conduct a follow up interview and survey after approximately 4 weeks.

All interviews will be completed through Zoom using a semi-structured interview guide developed by the research team based on the Consolidated Framework for Implementation Research The interviews will be conducted by the research assistant and a trained interviewer and recorded. The recordings will be transcribed for qualitative template analysis to identify major themes.

During the follow-up session, participants will also complete an electronic survey to assess the following feasibility concepts: acceptability of workbook, self-efficacy, Lynch Syndrome knowledge, Lynch Syndrome perceived knowledge, cost of workbook use.

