#### Interview Questions:

1. Is the workbook effective in enhancing your knowledge of cascade screening (the process of testing family members for Lynch syndrome)?
2. What positive or negative effects have you experienced in using the workbook?
3. Would you recommend the workbook to other patients? Why or why not?

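### The team that developed the workbook also collects its acceptability ratings, with no stated separation from the interviewer, so courtesy or acquiescence could inflate the single-arm comparison with 80%

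*Combined protocol and SAP*

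**What the plan says.** **Who made the workbook.** Section 1.1: "The research team developed the workbook in a previous project using implementation science strategies".

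**Who evaluates it.** Section 4.2: "The UNC research team will complete the follow up interview and survey with patients approximately 4 weeks after they received the workbook". On the interviews, section 4.6 says: "The interviews will be conducted by the research assistant and a trained interviewer and recorded". It does not say whether either person had a part in writing the workbook.

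**How the ratings are given.** Section 4.2: "All follow up surveys for patients will be conducted electronically in REDCap". Section 4.6: "During the follow-up session, participants will also complete an electronic survey to assess the following feasibility concepts". Section 4.7.2 also places the survey in that session. The plan does not say whether staff are on the call while the form is filled in, whether the interviewer can see the answers, or whether the survey comes before or after the interview. Section 7.1 adds that the interviews run without video.

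**What patients are told.** On the counselor route, section 4.2 says: "The genetic counselor will notify the patient that the workbook creators are interested in hearing feedback on the workbook use". Patients from Lynch Syndrome International (LSI) answer an advertisement instead, and no such notice is described for them.

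**What is tested.** Section 4.7.2 scores acceptability on seven items from 1 to 5, takes more than 80% as acceptable, and compares the scores with that level by a one-sample Wilcoxon signed rank test. In 9.2 all seven items are favourable statements rated for agreement, and none is reversed.

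**The interview guide (9.1).** The first question under Theme #2 is "Is the workbook effective in enhancing your knowledge of cascade screening". The interviews go to the template analysis and not to the Wilcoxon test.

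**The concern.** People asked to rate a product by those who made it may soften criticism (courtesy). People asked to agree with a run of favourable statements may lean towards agreeing (acquiescence). In 9.2 both would push the score the same way.

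The design has nothing to offset such a push. There is one arm and a fixed threshold, so any upward shift goes straight into the comparison with 80%. Acceptability is also the tested scale that rates the workbook itself. By item mean it has a higher bar than the other two scales scored 1 to 5. Section 1.3 says the results will inform a later R01 application, so an inflated acceptability finding would carry forward.

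The leading question in Theme #2 is a separate and smaller matter, because it bears only on the qualitative evidence about demand.

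**Working it through.** **1. The plan's own figure.** Section 4.7.1 justifies 15 patients by thematic saturation. It gives no alpha, sidedness, power, SD or effect size, so there is no power calculation to reproduce.

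**2. The threshold.** Seven items scored 1 to 5 give a total of 7 to 35.
- Percent of maximum: 0.80 × 35 = 28, an item mean of 28/7 = 4.0.
- Rescaled to 0-100: 7 + 0.80 × (35 − 7) = 29.4, an item mean of 29.4/7 = 4.2.

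The plan does not say which is meant; 28 is used below. For comparison, the self-efficacy threshold of 15 over 5 items and the perceived-knowledge threshold of 21 over 7 items are both an item mean of 3.0.

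**3. What a shift does to the score.**
- 0.25 point per item: 7 × 0.25 = 1.75 points; 1.75/35 = 5 percentage points.
- 0.50 point per item: 7 × 0.50 = 3.5 points; 3.5/35 = 10 percentage points.

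**4. What a shift does to the test.** The true mean is set at exactly 28, so a finding above 80% would be wrong. Total scores are simulated as normal, rounded and limited to 7-35, with n = 15. The entries are the chance of a significant result in the upper direction at two-sided 0.05.

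| Assumed shift per item | Mean of observed scores before capping | SD 4 | SD 5 |
|---|---|---|---|
| 0 | 28 | 0.022 | 0.023 |
| 0.25 | 29.75 | 0.337 | 0.215 |
| 0.50 | 31.5 | 0.860 | 0.667 |

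**5. Cross-check without rounding or capping.** With 15 untied scores the exact upper-tail critical value is W+ ≥ 95 (p = 0.0240) for a two-sided 5% test and W+ ≥ 90 (p = 0.0473) for a one-sided one. With 40,000 simulated trials per setting, the ranges from SD 6 to SD 3 are:

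| Assumed shift per item | Two-sided 0.05, upper tail | One-sided 0.05 |
|---|---|---|
| 0.1 | 6-13% | 11-21% |
| 0.2 | 12-38% | 20-51% |
| 0.3 | 23-69% | 34-80% |

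**What this shows.** The SDs, shifts, alpha and sidedness are all assumed. The tables show how sensitive the comparison would be to a shift of this kind. They say nothing about whether one exists, and any other upward bias of the same size would give the same figures.

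**6. The interview guide.** One question is closed and affirmative. Against it, the guide asks what patients disliked, whether the workbook was complex or easy, whether its length was right, which parts were hard, whether the format was a barrier, what negative effects they had, and what could have gone better in talking with a relative. The Theme #2 introduction also leaves open whether the workbook was of value at all.

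**The case against.** The case on the other side is substantial, and it rules out several stronger readings that a reader might infer.

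- **That the interview guide biases the 80% test.** It does not enter that test, which uses only the seven survey items. It could affect the ratings only if the interview came first, and the order is not stated.
- **That the guide as a whole is leading.** It is not; step 6 above shows one leading question among many that invite criticism.
- **That patients rate the workbook in front of its authors.** The survey is an electronic form that participants fill in, the interviews have no video, and the interviewers are not said to be the authors. This lowers the pressure. It does not establish privacy, because the form still belongs to a session run by the developing team.
- **That every patient is told the creators want feedback.** The notice is described for the counselor route only. The version 7.0 entry in the summary of changes says LSI recruitment was given priority and no patients came from OSU. Enrollment and follow-up by the UNC team do apply to both routes.
- **That the acceptability result is biased.** The documents support a risk and give no measure of it.

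It can also be said that this is a formative pilot of 15, that passing 80% only suggests acceptability, and that no go/no-go rule hangs on it. That stands and limits the consequence. It is not a reason to leave out a safeguard that costs almost nothing.

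**Conclusion.** The concern holds as a risk that the plan leaves open. The developing team collects uniformly favourable ratings in its own follow-up session, with no stated separation from the interviewer, and compares them with a fixed 80% in a single arm. If the true mean is 28/35 and the SD is 4 to 5, a shift of 0.25 point per item would raise the chance of a significant result above 80% from about 2% to 21-34%; a shift of 0.5 would raise it to 67-87%, allowing for small differences between simulation runs. These figures rest on n = 15, two-sided 0.05, 80% read as percent of maximum, and assumed SDs and shifts.

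The leading question in Theme #2 is a separate, minor defect of the qualitative evidence. This is a worthwhile, inexpensive improvement and does not invalidate the study.

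**What to change.** 1. In 4.2 and 4.6, state that the patient completes the 9.2 ratings alone through a REDCap link, with no interviewer on the call, and that the interviewer cannot see the ratings until that interview is coded.
2. Head the form with a statement that critical answers are as useful as favourable ones.
3. Reword the first Theme #2 question to: *How, if at all, did the workbook change what you know about cascade screening?*
4. Put the referral notice in neutral terms but keep the developers' role disclosed. Removing it would sit badly with the commitment in 7.2 to explain the study fully before consent.
5. If data collection is complete, report how the ratings were obtained (who was present, who could see them, and whether before or after the interview) and give possible upward bias as a limitation.

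These steps address courtesy. They leave the seven items as worded, so possible acquiescence belongs in the limitations either way.

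**Cost.** Changes to the referral, form and guide wording with the same staff; an amendment that the IRB must approve before use (7.4); and an occasional reminder when a survey is not returned.
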